
## Statistical Analysis Plan

As in our pilot study, we will define “likely cognitive impairment” as a score  $\leq 2$  on the MiniCog; while we are aware it is by no means a gold standard, it is based on a well validated cutoff that serves our purpose of identifying patients who may need special approaches during the perioperative period. All analyses will be repeated in the subset of individuals with the greatest degree of cognitive impairment based upon a MiniCog score of (0-1) in order to understand why these individuals were not identified as cognitively impaired. We will first test the sensitivity of standard procedures compared to systematic procedures with MiniCog defined impairment or severe impairment. We will also compare sensitivity and specificity of the standard vs. systematic approach, and vs. the published sensitivity of 75% in comparable populations. As a secondary outcome, we will try to understand the full relationship among our four assessments, for instance whether systematic chart review and patient/informant reports detect individuals not detected by standard MiniCog cutoffs, as such individuals would be important to include as part of a broad “impairment” outcome for Aim 2 and consider in subsequent work for special care in the perioperative period. Similarly, if we see patients who have received a formal evaluation of cognitive status in a memory clinic, by a primary care physician, or neuropsychological testing, we will try to understand qualitatively how MiniCog scores compare to such evaluations. Another secondary outcome will be how well patient/informant report can augment chart review when the patient does not have a primary care physician within our network. Differences between sensitivities and specificities will be compared using standard methods using confidence intervals. We will use logistic regression with any delirium as the outcome and cognitive impairment as defined by the MiniCog cutoff (or level of cognitive function as defined by the ordinal MiniCog score, modeled as best fits the data) in univariate analyses and in multivariate models adjusting for demographics (age, gender, education), baseline functional and medical covariates (ASA functional status, Charlson Comorbidity Index, METs, frailty). Analogous analyses for our secondary outcomes will use logistic, linear, or Cox proportional hazards models to assess the relationship of MiniCog scores to these outcomes. In univariate analyses, we will compare change in WHODAS in MiniCog-impaired vs. unimpaired patients using Wilcoxon U test and with ordinal MiniCog score using Spearman rank order correlation. Multivariate analyses will model change in WHODAS (ranked or transformed for best model fit) as a function of MiniCog impairment status (or ordinal value as above), controlling for age, gender, education, comorbidity index, and frailty. In exploratory analyses, patients with and without postoperative delirium will be analyzed separately and compared. Assays performed using blood collected from the current study will be analyzed in the grant “Circulating Extracellular Vesicles as Biomarkers of Postoperative Delirium” (grant submission number 1R21 AG061696-01). The grant has now received funding. [name], is the PI of the above grant; no changes to the current protocol will be made for this analysis. As a secondary analysis using variables collected during the course of the open enrollment phase of the study, a machine learning algorithm will be designed, to attempt to create a meaningful predictive model of postoperative delirium detection. This secondary use of data will explore the value of machine learning in anesthesiology, and its potential in predicting postoperative delirium.

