**Subject Enrollment:** The Brigham and Women's Hospital is the only study site. Study staff will use the CPE computerized scheduling system, which is updated continuously in real time and captures relevant information such as age and procedure, to identify potential subjects. When patients check in with the receptionist in the CPE for their appointment, they will be notified that they (and their surrogate) may be eligible to participate in a study in the CPE involving patients over the age of 65 or between the ages of 45-60. The receptionist will then provide them with a brochure about the study that includes information about the purpose of the study, the risks to the patient, and the potential benefits to society. The patient will then be asked if they are willing to speak with one of the study investigators and only those patients that agree to speak with a study investigator will be approached. Patients with known cognitive impairment will be included in the study to determine whether this information is included in the preoperative evaluation form. They will sign their own consent if they are capable and going to sign their surgical procedure consent. In the event that the patient is not capable of signing their own consent a surrogate will be asked to provide consent with assent from the patient. In our prior studies with similar patient populations less than 1% had documented cognitive impairment. The staff member will then describe the goals and risks of the study in a quiet room in the PATC and ask the patient (and their surrogate where appropriate) if they choose to participate. After all questions have been answered and the patient has the opportunity to read the consent form, written consent will be obtained by one of the study investigators.

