complete and has little or no education, language, or race bias. In addition, the Animal Fluency test will be administered, which is a short cognitive screen that takes one minute to complete. Other measures of cognitive impairment will be obtained by study staff through: documentation on the patient's standard preoperative form, patient or informant report of diagnosis or evaluation for cognitive impairment or memory concerns, and systematic medical record review. During their routine preoperative blood draw the phlebotomist will be provided with one 10mL heparinized blood tube, one 5mL heparinized blood tube and one 5mL non heparinized blood tube labeled with only the patient's study ID number that will be returned to the investigative team and processed within 30 minutes of the blood draw. If the phlebotomist is not able to obtain a sample during the patient's preoperative appointment, a sample will be drawn by a study staff member trained by one of the anesthesiologists, or a nursing or physician member of the anesthesiology team prior to incision instead. 20mL of blood will also be obtained after surgery in the PACU and also on postoperative day 1 by a study staff member trained by one of the anesthesiologists, or a nursing or physician member of the anesthesiology team. Total, the proposed collection is 60mL. However, the additional 20mL blood sample on post-op day 1 will only be collected if the Hematocrit level is 0.30 or higher. Briefly, half of the sample would be spun down and plasma harvested and stored at -80 degrees C and when an adequate sample size obtained used to measure inflammatory cytokines by ELISA. The remainder of the sample will be divided into 1-ml aliquots and incubated at 37°C for 15 min with phosphatebuffered saline (PBS) (control), 100 ng/ml interleukin (IL)-6, 100 ng/ml IL10, or a combination of 100 ng/mlIL-2 and 2 ng/ml granulocyte macrophage colony-stimulating factor, or 1g/ml lipopolysaccharide. Blood samples will be resuspended in 1.4 ml stabilizing buffer and incubated for 10 min at room temperature for fixation in PFA, cooled to 4C, and stored at 80C until further processing for flow cytometry to determine the immune response of the white blood cells to a ex-vivo immune challenge and whether these correlate with Mini-Cog score or the development of delirium. Each enrolled patient will receive a business card listing the investigators' contact information and be advised to expect a follow up telephone call prior to surgery to assess cognitive function and at 6 months and 1 year after surgery to verify data elements and reassess functional outcome. Delirium will be assessed prospectively twice per day (early afternoon, early evening) on postoperative days 1, 2, and 3 by a trained study team member using the Confusion Assessment Method [CAM]. Delirium is most common on postoperative days 1-3. For functional status, the WHODAS will be administered 6-12 months postoperatively, along with the Geriatric Depression Scale to assess mood, either by personnel in the surgeon's office as part of routine follow up or by study staff or by telephone. We will also collect information on secondary outcomes including duration of PATC visit, presence of an advanced directive, whether they had surgical procedure, time to PACU discharge, discharge to place other than home (rehabilitation, skilled nursing facility), hospital length of stay (LOS), in hospital complications, perioperative variables including drugs administered, BIS, estimated blood loss, blood transfusions, fluid administered, blood pressure, oxygen saturation, 30-day reoperation or readmission rate, and 30-day and 1-year mortality. These outcomes are recorded in the medical record, the BWH Balanced Scorecard, an electronic database of all hospitalized patients that tabulates 31 elements of the hospital event, or the BWH Research Patient Database Enhanced Query. Data will also be confirmed by a follow up telephone interview. Thirty day and 1 year mortality will be recorded.

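### Does comparing MiniCog-referenced sensitivity with a published 75% need a matched reference, a correction for MiniCog error, or a named paired method?

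*Combined protocol and SAP*

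**What the plan says.** The Statistical Analysis Plan defines likely impairment as a MiniCog score of 2 or less and says of this instrument: "while we are aware it is by no means a gold standard". All analyses are repeated for scores of 0 to 1. The first listed analysis is: "We will first test the sensitivity of standard procedures compared to systematic procedures with MiniCog defined impairment or severe impairment". The external comparison follows: "We will also compare sensitivity and specificity of the standard vs. systematic approach, and vs. the published sensitivity of 75% in comparable populations". The method given is: "Differences between sensitivities and specificities will be compared using standard methods using confidence intervals".

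The same section plans to study how the four assessments relate to each other. This includes whether chart review and reports find people MiniCog misses, of whom it says "such individuals would be important to include as part of a broad" impairment outcome. It also plans a qualitative comparison of MiniCog with formal cognitive evaluations where these exist.

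Under Study Procedures, the preoperative form, patient or informant report, and record review are introduced separately from MiniCog: "Other measures of cognitive impairment will be obtained by study staff through" these three routes. Under Subject Enrollment, the rate of known impairment is given: "In our prior studies with similar patient populations less than 1% had documented cognitive impairment".

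**The concern.** Sensitivity here means the share of MiniCog-positive patients that an approach flags. A patient whom MiniCog wrongly calls impaired counts as a miss for an approach that correctly leaves that patient unflagged. If the published 75% was measured against a clinical diagnosis, the two figures are different quantities. A result below 75% could then reflect poor detection, MiniCog false positives or a different case mix. A result above 75% could reflect errors shared with MiniCog. The section calls the populations comparable but says nothing about the references.

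A second worry is that standard and systematic procedures are scored in the same patients, yet the section does not say the comparison is paired. An unpaired interval could hide a real gain.

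**Working it through.** **The plan's own figure.** The 75% cannot be reproduced, because the documents give no inputs for it. The sample size of 250 has no calculation attached, so no power or precision claim depends on the 75%.

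**Standard form.** If the prior rate of under 1% carries over, fewer than 2.5 of 250 patients are documented. Over the assumed grid in the next step, MiniCog-positives number 30.0 to 91.2, so the form's sensitivity is at most 2.5/30.0 = 8.3%. It falls far short of 75% under any reference, so only the systematic approach is in question.

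**Size of a reference effect.** Let p be true prevalence, Se and Sp the MiniCog accuracy, and SeT and SpT that of the systematic approach. All these values are assumed.

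- Share MiniCog-positive: M = p·Se + (1−p)(1−Sp).
- Observed sensitivity = {p[SeT·Se + c₁] + (1−p)[(1−SpT)(1−Sp) + c₀]} / M, where c₁ and c₀ are error covariances in impaired and unimpaired patients.

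Base case: p = 25%, Se = SeT = 75%, Sp = SpT = 90%.

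- M = 0.1875 + 0.075 = 0.2625, about 66 of 250.
- Independent errors: (0.25×0.5625 + 0.75×0.01)/0.2625 = 56.4%.
- Error correlation 0.5 (c₁ = 0.5×0.1875, c₀ = 0.5×0.09): 0.2053/0.2625 = 78.2%.
- Error correlation 0.8: 0.2396/0.2625 = 91.3%.

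The true value is 75% throughout, so the shift runs from −19 to +16 points. With 66 MiniCog-positives and 56.4% observed, a 95% Wilson interval lies wholly below 75% with probability about 90%. If the published figure had used MiniCog in a population with similar prevalence and spectrum, both would read 56.4% and the gap would be zero.

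Grid: p = 10, 20, 30%; Sp = 80, 90, 95%; Se = SeT = 75%.

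| Assumption on the systematic approach | Observed sensitivity |
|---|---|
| No false positives, independent errors | 22.1–64.9% |
| No false positives, full overlap | 29.4–86.5% |
| 5% false positives, full overlap | 47.1–100% |

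The three 100% cells arise at Sp = 95%, where equal accuracy and full overlap make the approach identical to MiniCog. An upward shift does not depend on them: two other cells in that row (82.6%, 88.1%) and three in the row above exceed 75%.

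**Would a correction help?** Suppose 28 of 58 MiniCog-positives and 9 of 192 negatives are flagged. Observed sensitivity is 48.3% (exact 95% interval 35–62%). With independent errors and e = 1 − Sp, the corrected value is (28 − 37e)/(58 − 250e), because MiniCog sensitivity cancels:

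- Sp = 100%: 28/58 = 48.3%.
- Sp = 95%: 26.15/45.5 = 57.5%.
- Sp = 90%: 24.3/33 = 73.6%.

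At MiniCog sensitivity 75%, the implied predictive value of the approach is 1.010 at both Sp = 90% and Sp = 95%. It must be capped at 1, which gives 72.9% and 56.9%. All these estimates stay below 75%. They would cross it at e = 15.5/150.5 = 0.103, a specificity of 89.7%. The corrected answer is therefore set mainly by the specificity one assumes.

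**Pairing.** Suppose that of 58 MiniCog-positives the standard form finds 2 and the systematic approach finds 8, including those 2. Six pairs are discordant, all one way, so exact McNemar p = 2×0.5⁶ = 0.031; an unpaired Fisher test gives 0.094. If the two sets do not overlap, the discordant pairs split 8 to 2 and McNemar p = 0.109. At 28 against 2, Fisher p is about 2×10⁻⁸ and pairing is immaterial. The 8 of 58 that makes pairing matter is itself far below 75%, so one data set does not show both problems.

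**The case for a change.** The strongest case for a change is that admitting an imperfect reference is not the same as handling it. The benchmark sentence carries no caveat, this is the first analysis listed, and a reader given 48% against 75% will conclude that detection is poor. The repeat at scores 0 to 1 does not settle the matter. With assumed MiniCog sensitivity 50%, specificity 95–99% and p = 10–30%, an approach with true sensitivity 75% and no false positives shows 0.75 × PPV = 39.5–71.7% under independent errors and PPV = 52.6–95.5% under full overlap, on about 15 to 46 patients. The remedy would cost only wording and a small analysis of data already collected.

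Part of this stands: a gap from 75% cannot be read as detection performance alone unless the references match. But the section does not even say whose sensitivity the 75% is. It could belong to MiniCog, to a systematic approach or to usual care, and on the first reading a same-reference condition would not apply. Requiring a match or a correction presumes one reading of an unnamed source. Relabelling sensitivity as percent agreement would change no estimate, since the reference is already named and its weakness stated. The 90% chance of a falsely low interval applies a decision rule that the plan does not contain.

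On whether the systematic approach might include MiniCog, and so reach 100% by construction under an any-positive rule, the separate listing in Study Procedures and the count of four assessments point to MiniCog being kept apart.

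**Conclusion.** No change to the plan is needed. The documents show an unidentified benchmark, not a mismatched one, and nothing in this single-centre observational study is decided by it. The main contrast, standard against systematic, uses one reference in one cohort and remains valid as relative agreement with MiniCog. The external comparison can be presented descriptively, with the source's test and reference named, which a competent analyst would do at reporting.

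The possible distortion is large: −19 to +16 points in the base case and 22% to 100% over the grid, for a true 75%. Every figure in that range rests on assumed prevalence, MiniCog accuracy and error overlap, so a prespecified correction would replace one uncertain comparison with another that statisticians could equally dispute.

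Paired methods are the standard choice for two procedures scored in the same patients, and the stated method does not exclude them. That silence is a missing detail rather than an error. The conclusion would need another look if a study report used 75% as a pass mark or analysed the two procedures as independent samples; the documents propose neither.

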## Study Protocol

**Subject Selection:** This project is designed as a prospective, single-center observational study. The cohort will consist of 250 consenting subjects  $\geq$  65 years of age who present to the BWH Weiner Center for Preoperative Evaluation (CPE) prior to elective lower extremity joint replacement surgery. These surgeries are selected because they are common in this age group, associated with significant morbidity, and along with dementia are considered a priority area (bone and joint conditions) by AHRQ. These ages are chosen as significant clinical data demonstrate increased cognitive impairment in community dwelling elders. Eligibility criteria include: patients  $\geq$  65 years of age with an ASA physical status of I-IV presenting for elective joint replacement or non-cancer spine surgery. Exclusion criteria will include planned ICU admission postoperatively, history of stroke or brain tumor, uncorrected vision or hearing impairment (unable to see pictures or read or hear instructions); limited use of the dominant hand (limited ability to draw); and or inability to speak, read, or understand English.

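### Does the lack of a rule for CAM assessments not done leave the any-delirium analysis open to bias?

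*Combined protocol and SAP*

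**What the plan says.** Under Study Procedures, the Study Protocol states: "Delirium will be assessed prospectively twice per day (early afternoon, early evening) on postoperative days 1, 2, and 3". That is 2 × 3 = 6 planned assessments per patient. It mentions no assessment after discharge, but does not say that assessment stops there.

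The Statistical Analysis Plan reduces these six to one binary outcome: "We will use logistic regression with any delirium as the outcome". MiniCog impairment (or the ordinal score) is the exposure, with multivariate models "adjusting for demographics (age, gender, education), baseline functional and medical covariates (ASA functional status, Charlson Comorbidity Index, METs, frailty". Neither length of stay nor the number of assessments completed is in that list. The plan sets no minimum number of assessments and gives no general missing-data rule.

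Length of stay is collected as a secondary outcome, and secondary outcomes are to be analysed with logistic, linear or "Cox proportional hazards models to assess the relationship of MiniCog scores to these outcomes". Study Procedures also records "whether they had surgical procedure, time to PACU discharge", so some enrolled patients may have no operation. The delirium label is used again in an exploratory analysis, where "patients with and without postoperative delirium will be analyzed separately and compared".

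**The concern.** At least three codings are compatible with the text:

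- **Any positive among those done.** Assessments not done count as negative.
- **Drop early negatives.** A patient who leaves early is kept if positive and set to missing otherwise.
- **Full window only.** Only patients assessed through postoperative day 3 are analysed.

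If assessment ends at discharge and impaired patients stay longer, they have more chances to be found positive. The first rule then pushes the odds ratio up and the second pushes it down. The third does nothing if discharge is unrelated to delirium, and pushes it down if delirium keeps patients in hospital. A rule chosen after the data are seen could therefore affect the main delirium result and the exploratory comparison built on the same label. The plan does not assume equal stay, since it models its secondary outcomes, length of stay among them, on MiniCog score.

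**Working it through.** The plan gives no delirium rate, stay distribution, missed-assessment rate or power figure, so there is no figure of its own to reproduce. From the documents come the six assessments, the covariates and the sample size ("The cohort will consist of 250 consenting subjects"). Everything else below is assumed.

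**Crude odds ratios with no true association.** Patients leave after day 1, after day 2, or stay through day 3, giving 2, 4 or 6 assessments. The risk of a first positive per assessment is h. For a group with shares s₂, s₄, s₆:

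- P_k = 1 − Π(1 − h_j) over k assessments; positives = Σ s_k P_k
- odds, any positive among those done = positives / (1 − positives)
- odds, drop early negatives = positives / [s₆(1 − P₆)]
- odds, full window only, discharge unrelated to delirium = P₆ / (1 − P₆)

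Worked case: h = 0.04 throughout; impaired 10/25/65%, unimpaired 25/35/40%.

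- P₂ = 1 − 0.96² = 0.0784; P₄ = 1 − 0.96⁴ = 0.1507; P₆ = 1 − 0.96⁶ = 0.2172
- Impaired positives = 0.10 × 0.0784 + 0.25 × 0.1507 + 0.65 × 0.2172 = 0.1867
- Unimpaired positives = 0.25 × 0.0784 + 0.35 × 0.1507 + 0.40 × 0.2172 = 0.1592
- Any positive among those done: (0.1867/0.8133) / (0.1592/0.8408) = 1.21
- Drop early negatives: [0.1867/(0.65 × 0.7828)] / [0.1592/(0.40 × 0.7828)] = 0.72
- Full window only: 1.00. If every positive patient is kept through day 3, this rule equals the previous one, 0.72.

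The table covers three assumed stay gaps. The second value in each cell uses front-loaded risk (0.05, 0.05, 0.025, 0.025, 0.015, 0.015).

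| Impaired vs unimpaired stay (%) | Any positive among done | Drop early negatives |
|---|---|---|
| 10/30/60 vs 15/40/45 | 1.10; 1.05 | 0.81; 0.78 |
| 10/25/65 vs 25/35/40 | 1.21; 1.11 | 0.72; 0.67 |
| 5/20/75 vs 40/35/25 | 1.53; 1.26 | 0.47; 0.41 |
| equal stay | 1.00 | 1.00 |

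**With a true association.** Doubling the odds of each assessment in impaired patients gives a six-assessment odds ratio of 2.22 (flat) or 2.15 (front-loaded). Over the three unequal gaps, any positive among those done gives 2.36–3.33 or 2.23–2.69. Dropping early negatives gives 1.06–1.82 or 0.88–1.69. Of these twelve values, one is below 1.

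**Which group stays longer.** A separate enumeration took true risks of 12% and 24% (odds ratio 2.32) and last hospital days of 20/40/40% or 5/25/70%. Counting those done gave 2.62 when impaired patients stayed longer and 1.96 when they stayed shorter. Dropping early negatives gave 1.49 and 3.59. The direction thus depends on the sign of the stay difference as well as on the rule.

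**Frailty-adjusted null odds ratios by simulation** (25% impaired):

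- Stay depends on MiniCog only through frailty: 1.00–1.02 under every rule.
- Stay depends on MiniCog directly (mean 5.0 or 5.4 assessments vs 4.3): 1.09–1.31 for any positive among those done; 0.58–0.75 for dropping early negatives; full window 0.99–1.02 if discharge is independent of delirium, 0.58–0.75 if delirium delays it.
- Stay extended to the day of first positive, so that patients about to turn positive are never sent home first: 0.99–1.01, 0.52–0.65 and about 0.76–0.89 respectively.

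**Size against sampling error.** The standard error of the log odds ratio at 250 patients is 0.38–0.42 in these simulations. For any positive among those done, ln 1.09 / 0.42 = 0.2 and ln 1.31 / 0.38 = 0.7. The false-positive rate in the direct-stay cases was 5.9–11.3% against a nominal 5%. With 2,000 replicates the Monte Carlo margin is 1.96 × √(0.05 × 0.95/2000) = 0.96 points, so the front-loaded values (5.9% and 6.0%) are at its edge.

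**The case for a change.** The strongest case for a change is cost. Two or three sentences and one table of completed assessments by MiniCog group would close off a choice made after seeing the data. The label feeds the first outcome regression in the plan and later analyses, and under the same assumed data the estimate can fall on either side of 1. All of that is arithmetically right, and such a table would be a sensible thing to report.

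It does not show that the planned analysis is wrong. The three codings are not equally natural. Any delirium, from repeated assessments, ordinarily means at least one positive among those done. Dropping early leavers only when negative selects on the outcome, and nothing in the plan points to it. The low odds ratios come from that rule, or from the full-window rule when delirium delays discharge. Patients without surgery have no postoperative days, so they fall outside this outcome without a further rule.

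Restricting a sensitivity analysis to day 1 would give null values of 0.99–1.02 in the direct-stay cases, but at a price: about 20–25 events instead of 37–44, a standard error of 0.50–0.55 instead of 0.38–0.42, and a narrower question. Its window is also common to both groups only if nobody leaves before the day 1 evening assessment, which the modelling assumed. That is a trade-off rather than a correction.

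**Conclusion.** No change to the plan follows. The coding rule is missing detail that an analyst would fill sensibly with any positive among the assessments done, and stating it would leave the results as they would have been.

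Under that reading, the illustrative adjusted null odds ratio is about 1.1 to 1.3 if three things hold: assessment stops at discharge, impaired patients stay longer for reasons the covariates do not capture, and patients about to turn positive are sometimes discharged first. It is about 1.0 if the second or third fails, and the direction reverses if impaired patients stay shorter. If the target is delirium detected in hospital, unseen days need no correction. The documents give no data on stay or delirium rates, so neither the existence nor the size of any bias can be established from them.
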